20.0 APPENDICES

Appendix A: Requirements for REMS®

Risks of Fetal Exposure, Pregnancy Testing Guidelines and Acceptable Birth Control Methods

Requirements for REMS®

- Patients should be instructed never to give lenalidomide to another person.
- Patients will be asked to take part in a mandatory confidential survey prior to initiation of lenalidomide. To take the survey, they will be instructed to call the Celgene Customer Care Center at [name]. Male patients will be asked to take the survey monthly. Female patients will be asked to take survey periodically (monthly if females of childbearing potential and every 6 months if females of not childbearing potential).
- Female patients should not donate blood during therapy and for at least 28 days following discontinuation of lenalidomide.
- Male patients should not donate blood, semen or sperm during therapy or for at least 28 days following discontinuation of lenalidomide.
- Only enough lenalidomide for one cycle of therapy may be prescribed with each cycle of therapy. Monthly phone counseling is required per the REMS® program in order to prescribe a one-month supply of lenalidomide.
- All patients will be required to sign the REVLIMID, Patient-Physician Agreement Form.
- Males must practice complete abstinence or use a condom during sexual contact with pregnant females or females of childbearing potential throughout the entire duration of lenalidomide treatment, during dose interruptions and for at least 28 days following lenalidomide discontinuation and 90 days after the last dose of carfilzomib, even if he has undergone a successful vasectomy. Male patients must refrain from donating sperm for at least 90 days after the last dose of carfilzomib. See below for further details.

- Females of childbearing potential must agree to use two reliable forms of contraception simultaneously or to practice complete abstinence from heterosexual intercourse during the following time periods related to this study: 1) for at least 28 days before starting lenalidomide; 2) throughout the entire duration of lenalidomide treatment; 3) during dose interruptions; 4) for at least 28 days after lenalidomide discontinuation; and 5) for at least 30 days after the last dose of carfilzomib. See below for further details.

Females not of childbearing potential must sign the REVLIMID, Patient-Physician Agreement Form that says you are presently not pregnant and do not have the ability to have children.

Risks Associated with Pregnancy

The use of lenalidomide in pregnant females and nursing mothers has not been studied nor has the effect of the lenalidomide on human eggs and sperm. Lenalidomide is structurally related to thalidomide. Thalidomide is a known human teratogenic active substance that causes severe life-threatening birth defects. An embryofetal development study in animals indicates that lenalidomide produced malformations in the offspring of female monkeys who received the drug during pregnancy. The teratogenic effect of lenalidomide in humans cannot be ruled out. Therefore, a risk minimization plan to prevent pregnancy must be observed.

All study participants must be registered into the mandatory REMS® program, and be willing and able to comply with the requirements of REMS®.

Criteria for females of childbearing potential (FCBP)

This protocol defines a female of childbearing potential as a sexually mature female who: 1) has not undergone a hysterectomy or bilateral oophorectomy or 2) has not been naturally postmenopausal for at least 24 consecutive months (i.e., has had menses at any time in the preceding 24 consecutive months).

The investigator must ensure that:

- Females of childbearing potential comply with the conditions for pregnancy risk minimization, including confirmation that she has an adequate level of understanding
- Females NOT of childbearing potential acknowledge that she understands the hazards and necessary precautions associated with the use of lenalidomide
- Male patients taking lenalidomide acknowledge that he understands that traces of lenalidomide have been found in semen, that he understands the potential teratogenic risk if engaged in sexual activity with a female of childbearing potential, and that he understands the need for the use of a condom even if he has had a vasectomy, if engaged in sexual activity with a female of childbearing potential.

Contraception

Females of childbearing potential (FCBP) enrolled in this protocol must agree to use two reliable forms of contraception simultaneously or to practice complete abstinence from heterosexual intercourse during the following time periods related to this study: 1) for at least 28 days before starting lenalidomide; 2) throughout the entire duration of lenalidomide treatment; 3) during dose interruptions; and 4) for at least 28 days after lenalidomide discontinuation.

The two methods of reliable contraception must include one highly effective method and one additional effective (barrier) method. FCBP must be referred to a qualified provider of contraceptive methods if needed. The following are examples of highly effective and additional effective methods of contraception:

- Highly effective methods:
 - Intrauterine device (IUD)
 - Hormonal (birth control pills, injections, implants)
 - Tubal ligation
 - Partner's vasectomy
- Additional effective methods:
 - Male condom
 - Diaphragm
 - Cervical Cap

Because of the increased risk of venous thromboembolism in patients with multiple myeloma taking lenalidomide and dexamethasone, combined oral contraceptive pills are not recommended. If a patient is currently using combined oral contraception the patient should switch to one of the effective methods listed above. The risk of venous thromboembolism continues for 4–6 weeks after discontinuing combined oral contraception. The efficacy of contraceptive steroids may be reduced during co-treatment with dexamethasone.

Implants and levonorgestrel-releasing intrauterine systems are associated with an increased risk of infection at the time of insertion and irregular vaginal bleeding. Prophylactic antibiotics should be considered particularly in patients with neutropenia.

Pregnancy testing

Medically supervised pregnancy tests with a minimum sensitivity of 50 mIU/mL must be performed for females of childbearing potential, including females of childbearing potential who commit to complete abstinence, as outlined below.

Before starting lenalidomide

Female Patients:

FCBP must have two negative pregnancy tests (sensitivity of at least 50 mIU/mL) prior to prescribing lenalidomide. The first pregnancy test must be performed within 10-14 days prior to prescribing lenalidomide and the second pregnancy test must be performed within 24 hours prior to prescribing lenalidomide. The patient may not receive lenalidomide until the Investigator has verified that the results of these pregnancy tests are negative.

Male Patients:

Must agree to practice complete abstinence or agree to use a condom during sexual contact with pregnant females or females of childbearing potential throughout the entire duration of lenalidomide treatment, during dose interruptions and for at least 28 days following lenalidomide discontinuation, even if he has undergone a successful vasectomy.

During study participation and for 28 days following lenalidomide discontinuation

Female Patients:

- FCBP with regular or no menstrual cycles must agree to have pregnancy tests weekly for the first 28 days of lenalidomide treatment, including dose interruptions and then every 28 days throughout the remaining duration of lenalidomide treatment, including dose interruptions, at lenalidomide discontinuation, and at Day 28 following lenalidomide discontinuation. If menstrual cycles are irregular, the pregnancy testing must occur weekly for the first 28 days of lenalidomide treatment, including dose interruptions, and then every 14 days throughout the remaining duration of lenalidomide treatment, including dose interruptions, at lenalidomide discontinuation, and at Day 14 and Day 28 following lenalidomide discontinuation.
- At each visit, the Investigator must confirm with the FCBP that she is continuing to use two reliable methods of birth control at each visit during the time that birth control is required.
- If pregnancy or a positive pregnancy test does occur in a study patient, lenalidomide must be immediately discontinued.
- Pregnancy testing and counseling must be performed if a patient misses her period or if her pregnancy test or her menstrual bleeding is abnormal. Lenalidomide treatment must be temporarily discontinued during this evaluation.
- Females must agree to abstain from breastfeeding during study participation and for at least 28 days after lenalidomide discontinuation.

Male Patients:

- Must practice complete abstinence or use a condom during sexual contact with pregnant females or females of childbearing potential throughout the entire duration of lenalidomide treatment, during dose interruptions and for at least 28 days following lenalidomide discontinuation, even if he has undergone a successful vasectomy.

If pregnancy or a positive pregnancy test does occur in the partner of a male study patient during study participation, the investigator must be notified immediately.

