6.1 Subject Inclusion Criteria

- Newly diagnosed patients with histologically confirmed MM based on the following criteria:
 - Clonal plasma cells in the bone marrow
 - Measurable disease within the past 4 weeks defined by any one of the following:
 - Serum monoclonal protein ≥ 1.0 g/dL
 - Urine monoclonal protein >200 mg/24 hour
 - Involved serum immunoglobulin free light chain > 10 mg/dL AND abnormal kappa/lambda ratio
- Evidence of underlying end organ damage and/or myeloma defining event attributed to underlying plasma cell proliferative disorder meeting at least one of the following:
 - Hypercalcemia: serum calcium >0.25 mmol/L (> 1 mg/dL) above upper limit of normal or ≥ 2.75 mmol/L (11 mg/dL)
 - Anemia: hemoglobin value <10 g/dL or > 2 g/dL below lower limit of normal
 - Bone disease: ≥ 1 lytic lesions on skeletal X-ray, CT, or PET-CT. For patients with 1 lytic lesion, bone marrow should demonstrate $\geq 10\%$ clonal plasma cells
 - Clonal bone marrow plasma cell percentage $\geq 60\%$
 - Involved/un-involved serum free light chain ratio ≥ 100 and involved free light chain >100 mg/L.
 - > 1 focal lesion on magnetic resonance imaging study (lesion must be >5 mm) in size
- Creatinine Clearance ≥ 60 ml/min. CrCl can be measured or estimated using Cockcroft-Gault method, MDRD, or CKD-EPI formulae
- Age ≥ 18 years at the time of signing the informed consent documentation
- Eastern Cooperative Oncology Group (ECOG) performance status 0-2
- Absolute neutrophil count (ANC) ≥ 1.0 K/uL, hemoglobin ≥ 8 g/dL, and platelet count ≥ 75 K/uL, unless if cytopenias are deemed to be due disease at discretion of clinical investigator. Transfusions and growth factors are permissible.
- Adequate hepatic function, with bilirubin < 1.5 x the ULN, and AST and ALT < 3.0 x ULN.

- All study participants must be able to tolerate one of the following thromboprophylactic strategies: aspirin, low molecular weight heparin or warfarin (coumadin) or alternative anti-coagulant.
- All study participants must be registered into the mandatory eREMS® program, and be willing and able to comply with the requirements of REMS®.

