Different kinds of infection have been seen in patients receiving daratumumab. Most of them are upper respiratory tract infection. Majority of the observed infections so far were mild or moderate. Severe infection such as pneumonia and sepsis has also been reported. Herpes Zoster Virus infection (shingles) is an uncommon finding. Your doctor will tell you about how to prevent the Herpes Zoster Virus infection.

Indirect Antiglobulin Testing

If you need a blood transfusion, tests are performed on your blood so that suitable donor blood can be given for a transfusion. Daratumumab treatment will affect one of these tests known as an indirect antiglobulin test (IAT; also known as an indirect Coombs test). Therefore, an IAT will be done before you receive daratumumab and the result placed on the patient identification wallet card you will carry for this study. Before a blood transfusion, you should show the wallet card and tell all your health care

providers that you are taking daratumumab and that it interferes with pre-transfusion blood testing. You should do this during the entire period that are receiving daratumumab and for at least 6 months after your last daratumumab infusion or for as long as your study doctor recommends.

What about birth control and pregnancy during the study?

The effects of daratumumab on fertility, the human embryo, the fetus, or the breast-fed infant are unknown. If you are a woman, taking part in the study might harm your unborn child or breast-fed baby. Thus, you must agree not to become pregnant while you are in this study. Also, you cannot take part in this study if you are pregnant or breastfeeding a child. If you are a man, the effect of daratumumab on your sperm is unknown.

If you are a woman and becoming pregnant is a possibility, you will be required to undergo a pregnancy test prior to taking daratumumab. Both male and female patients must use effective methods of birth control during the course of the study and for 3 months after stopping daratumumab.

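### Appendix A's contraception list for women of childbearing potential leaves out the 3 months after daratumumab that section 11.4 requires

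*Combined protocol and SAP*

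**What the plan says.** Section 11.4 (Daratumumab) sets a rule for both sexes: they "must use effective methods of birth control during the course of the study and for 3 months after stopping daratumumab".

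Appendix A, in its opening bullets, requires women of childbearing potential to use two forms of contraception or abstain "during the following time periods related to this study". The list has five items, and the post-treatment ones read "for at least 28 days after lenalidomide discontinuation; and 5) for at least 30 days after the last dose of carfilzomib". Daratumumab is not mentioned. The bullet refers the reader to further details below. There, under Contraception, the list is repeated for women enrolled in the protocol, but it stops at "and 4) for at least 28 days after lenalidomide discontinuation". That version names neither carfilzomib nor daratumumab.

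For men, the opening bullets of Appendix A require condoms or abstinence for at least 28 days "following lenalidomide discontinuation and 90 days after the last dose of carfilzomib, even if he has undergone a successful vasectomy". Appendix C also gives men 90 days after carfilzomib. The two Male Patients paragraphs later in Appendix A, one for the time before lenalidomide starts and one for study participation, give only the 28 days after lenalidomide. No male paragraph in Appendix A has a daratumumab period.

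Two other places lead readers to Appendix A. Footnote e of the section 10.0 schedule cites it for pregnancy testing and birth control, and section 6.1 requires patients to "be willing and able to comply with the requirements of REMS".

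**The concern.** Appendix A is titled as the lenalidomide REMS requirements, so a list confined to lenalidomide would be no surprise. The list for women is not confined in that way. It describes its periods as those related to this study, and it adds a carfilzomib item. Having gone beyond lenalidomide, it leaves out the drug with the latest end date for women. Nothing in the documents says that the latest date governs.

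Appendix A also asks the investigator to confirm at each visit that a woman is using two methods for as long as birth control is required. That check depends on a correct end date, and the appendix gives one that is too early. Section 11.4 describes daratumumab's effects on the embryo and fetus as unknown, so the 3-month period is precautionary, but it is mandatory as written.

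**Working it through.** The plan gives no figure to reproduce. The check counts when each period ends, in days from day 1 of the last cycle given.

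**Inputs (section 9.0 dosing, planned schedule)**
- Last lenalidomide dose: day 21.
- Last carfilzomib dose: day 16 (cohort 1) or day 15 (cohort 2).
- Last daratumumab dose: day 22 in cycles 1–2, day 15 in cycles 3–6, day 1 in cycles 7–8.
- Assumption: 3 calendar months is 89 to 92 days, depending on the start date.

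**Women, Appendix A**
- Lenalidomide: 21 + 28 = 49.
- Carfilzomib: 16 + 30 = 46 or 15 + 30 = 45.
- The later date is day 49 in both cohorts. Dropping carfilzomib from the repeated list therefore changes no date on the planned schedule.

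**Women, section 11.4 against Appendix A**

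| Last cycle given | Last daratumumab | Section 11.4 ends | Minus day 49 |
|---|---|---|---|
| 8 | day 1 | 1 + 89 to 1 + 92 = 90–93 | 41–44 days (about 6 weeks) |
| 4 | day 15 | 15 + 89 to 15 + 92 = 104–107 | 55–58 days (about 8 weeks) |
| 1 or 2 | day 22 | 22 + 89 to 22 + 92 = 111–114 | 62–65 days (about 9 weeks) |

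Sensitivity: if lenalidomide discontinuation is dated at the end of the 28-day cycle instead of day 21, Appendix A ends on 28 + 28 = 56. The gap after cycle 8 becomes 90 − 56 = 34 to 93 − 56 = 37 days.

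**Men, carfilzomib period**
- Opening bullets of Appendix A: 16 + 90 = 106 (cohort 1) or 15 + 90 = 105 (cohort 2).
- Later male paragraphs read alone: 21 + 28 = 49.
- Difference: 106 − 49 = 57 or 105 − 49 = 56 days.

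**Men, daratumumab period against the 90-day carfilzomib rule**
- After cycle 8: section 11.4 ends on day 90–93, so the carfilzomib rule runs 12–16 days past it.
- After cycle 4: section 11.4 ends on day 104–107, so the carfilzomib rule ends between 2 days after it and 2 days before it.
- After cycle 1 or 2: section 11.4 ends on day 111–114, so the carfilzomib rule falls short by 5–8 days (cohort 1) or 6–9 days (cohort 2).

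**The case against.** The strongest reply is that the safeguard is already in the protocol. Section 11.4 is mandatory and covers both sexes. The text is largely organised by drug: section 11.4 for daratumumab, Appendix A for lenalidomide, Appendix C for carfilzomib. Every period is a minimum, so a patient who follows all the clauses is covered. That stands, and it limits the point to what Appendix A says when used alone. It does not rescue the list for women, which already mixes drugs.

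The section 6.1 criteria add little. They give no post-treatment contraception period for any drug, so their silence on daratumumab shows nothing specific.

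The day counts hold only on the planned schedule. Section 9.0 allows ±7 days on cycle starts and ±2 days within cycles, and doses may be held. Section 4.2 lets patients go on to lenalidomide maintenance under another protocol. The 28-day clock would then not have started, and the gap for women may not arise.

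Three stronger readings are tempting, and the documents do not support them.
- A reader might infer that the male paragraphs contradict the 90-day rule. They omit it without denying it: 28 days after one drug and 90 days after another can both be obeyed.
- A reader might infer a donation conflict, since one Appendix A bullet says "Male patients should not donate blood, semen or sperm during therapy or for at least 28 days following discontinuation of lenalidomide" and another says "Male patients must refrain from donating sperm for at least 90 days after the last dose of carfilzomib". These too are compatible minimums. Section 11.4 bars egg and sperm donation for 3 months after the study drug, which in context is daratumumab.
- A reader might take the course of the study in section 11.4 to include the 3-year follow-up. The clause adding 3 months after daratumumab would then have no work to do, so that reading is strained.

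**Conclusion.** The point holds for women. Appendix A's list gives an end date that is too early against section 11.4, by about 6 weeks after cycle 8, about 8 weeks after a stop at cycle 4 and about 9 weeks after a stop at cycle 1 or 2. This assumes planned dosing days, lenalidomide stopping on day 21 of the last cycle and no lenalidomide afterwards.

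For men, the later paragraphs of Appendix A are an incomplete repetition of its own carfilzomib rule. The missing daratumumab period matters by at most 9 days, mainly after a stop at cycle 1 or 2.

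A clinician or patient relying on Appendix A alone could stop too early. It cannot be said that anyone would: the consent pages are not available, and the number of patients affected is not given. This is a minor inconsistency in patient-safety text. It does not touch the MRD endpoint, the Simon two-stage design or any analysis.

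**What to change.** In Appendix A, use one rule in the opening bullets, the Contraception paragraph and both Male Patients paragraphs. Contraception continues during treatment and until the latest of:
- 28 days after lenalidomide;
- 30 days (women) or 90 days (men) after carfilzomib;
- 3 months after daratumumab.

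Align the consent form if it differs. The cost is a wording-only amendment, with no extra visits or tests.

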APPENDIX B

To characterize bone marrow aspirate specimens for somatic base mutations and copy number alterations in key cancer-associated genes, we will perform a custom, targeted deep-sequencing assay on matched tumor and normal pairs. The assay, termed *myTYPE* involves massively parallel sequencing, coupled with solution-phase exon capture. The assay will generate high-depth (~1500x) sequencing data for genes causally implicated in myeloma pathogenesis by comprehensive whole exome and whole genome studies. Genes have been selected on the basis of known mutation frequencies in myeloma neoplasms and prior evidence from genomic profiling studies including copy number analysis. *myTYPE* contains genome wide copy number probes, which supports detection of arm level copy number alterations as well as hyperdiploid genomes and the detection of IGH rearrangements. Thus, using *myTYPE* we will establish in-house algorithms to deliver full genome annotation and definition of clonal and subclonal mutation clusters. For studies focusing on characterization of MRD+ cells, samples will be sorted of FACS-Aria Fusion and RNA and DNA will be extracted for bulk sequencing. Clonal architecture of residual disease will be evaluated by single cell transcriptome analysis. The targeted DNA sequencing panel *myTYPE* covers the following:

- Copy number analysis: by including genome wide SNPs at least every 3Mbs
- IgH translocations: by including the hotspot intron In IgH where the vast majority of breakpoints occur
- Amplifications and deletions: we are adding additional SNPs for common amplification and deletions in myeloma, both for chromosomal regions and specific genes i.e. 1q gain and 17p deletion, *MYC* amplification, *CKS1B* amplification, *TP53* deletion, and more.
- Genes (exons) with previously reported recurrent mutations, i.e. *KRAS*, *NRAS*, *BRAF*, *FAM46C*, *IRF4*, *TRAF3*, *TP53*, *CYLD*, *DIS3*, and many more (in total ~110 genes). In addition, we are adding previously mutated and candidate genes in treatment target pathways, i.e. the cereblon pathway, NFkB and BCR pathways, genes within proteasome subunits, as well as targets for novel immunotherapy.

APPENDIX C

Contraception/Female

FCBP patients should be advised to avoid becoming pregnant while being treated with carfilzomib. Given that carfilzomib was clastogenic in the in vitro chromosomal aberration test in peripheral blood lymphocytes, as a precaution, females of childbearing potential and/or their male partners should use effective contraception methods or abstain from sexual activity during and for 30 days after treatment with carfilzomib.

Contraception/Male

Males of reproductive potential should be advised to avoid fathering a child while being treated with carfilzomib. The potential for carfilzomib to be transferred via semen and its effect on sperm are unknown. Male subjects treated with carfilzomib and/or their female partners (if of childbearing potential) should use effective contraceptive methods or abstain from sexual activity while treated with carfilzomib for 90 days after treatment.
